3.6 Vulnerable Population

We will recruit 5 employees from each location for the hospital staff interviews and ensure additional safeguards for these subjects. Employees' participation is completely voluntary and without undue influence. Participants will be assured that their employment will not be affected by their decision to participate or not. Any record of staff's participation will not be linked to any type of employee record. None of the study's primary investigators or study team members have any supervisory or management role for the participants in this group nor do they have any effect on employees' evaluation.

4. METHODS AND PROCEDURES

4.2 Patient Participant Recruitment

We will recruit patients using 5 methods. First, we will place flyers (Appendix A) in the waiting rooms of the primary care clinics and social work clinics at each hospital and at the elevator banks on each floor. We will also distribute flyer advertisements in the AM New York and Metro, two free local papers (Appendix Z) and El Especialito, a Spanish local paper (Appendix A). Flyers will describe the study, primary eligibility criteria, and a phone number to call. Patients who call will be screened for eligibility by a trained Research Assistant (RA) over the phone (Appendix C). The RA will schedule eligible participants for an in-person appointment to complete an IRB-approved informed consent process. Additionally, we will advertise on Facebook to English and Spanish speaking smokers located in New York City (Appendix A).

Second, this study will utilize NYUMC DataCore to use the Bellevue and NYU Lutheran's EMR data to identify patients who were screened as current tobacco users during a clinical visit in the

last 12 months. We will need patients' names, date they were screened to be a smoker, contact information (phone, address), preferred language, primary care provider name, and primary health insurance. DataCore will request a report in order to gather the data from EPIC/QuadraMed. We would like this query to be completed 4 times (3 months apart). Only the PI, Research Coordinator and Research Assistants will have access to the EMR search results. For patients assigned a primary care provider in the EHR, the RA will email each patient's primary care provider via secure institutional email (Appendix X) to notify the provider that we be contacting their patient(s) about the study and give the provider the opportunity to let us know not to contact a specific patient. We will wait 4 business days after sending the email to hear back from the provider. If a provider tells us not to contact a patient, we will remove the patient from our recruitment list (destroying his/her identifiers). To all patients on our list who are not identified by a provider as someone we should not contact, the RA will send a letter (Appendix B) and recruitment flyer (Appendix A). One week after mailing the materials, an RA will call the patients to discuss the study, screen interested patients for eligibility, and schedule eligible participants for an appointment to complete an IRB-approved informed consent process. Patients without a primary care provider assigned in the EHR will immediately receive the letter and recruitment flyer in the mail. One week after mailing the materials, an RA will call these patients to discuss the study. The RA will inform these patients of how we received their contact information and also let them know that they do not currently have a PCP listed in their electronic medical record. All identifiable screener data for patients who are deemed ineligible or who do not wish to participate in the study will be destroyed. We will only keep itemized screener data to report to the funding agency, though no PHI will be saved and we will only label participants with a pre-screening number.

Third, at the Bellevue site, we will receive referrals from the hospital's regular smoking cessation program. The smoking cessation program will let patients know about the study and give them the study flyer (Appendix A). The program will ask if they are interested in being referred to our study to learn more about the study. For patients who give permission to be referred, the Bellevue smoking cessation program will send our study team an NYUMC encrypted email with the name and preferred contact information. To all referred patients, a study RA will send a letter (Appendix B) and the recruitment flyer (Appendix A). Two weeks after mailing the materials, an RA will call the patients to discuss the study, screen interested patients for eligibility, and schedule eligible participants for an appointment to complete an IRB-approved informed consent process. All identifiable screener data for patients who are deemed ineligible or who do not wish to participate in the study will be destroyed. We will only keep itemized screener data to report to the funding agency, though no PHI will be saved and we will only label participants with a pre-screening number.

Fourth, we will work with medical center IT to set up a consult in EPIC that allows physicians to refer Lutheran patients to the program. Providers will be given an overview of the study and eligibility criteria prior to implementing the EPIC consult, so that they may filter some of the referrals received. If a patient is deemed eligible for referral, physicians will inform their patients that someone from the study team will contact them within the next two weeks to screen for study eligibility. Providers will also have copies of our study flyer (Appendix A) to hand out to patients who are interested, so the patient may also reach out directly to the research coordinator as directed by the flyer. Each day, a study team member will check EPIC for a list of patients referred by their providers. An RA will contact the patients to screen for eligibility. Those who are eligible will be scheduled for a consent appointment. Patients who are ineligible to participate in the study will be referred to the NY State Quitline. All identifiable screener data for patients who are deemed ineligible or who do not wish to participate in the study will be destroyed. We will only keep itemized screener data to report to the funding agency, though no

PHI will be saved and we will only label participants with a pre-screening number. We will also use EPIC to reach out to potential patients using MyChart. We will utilize EPIC's Slicer Dicer research tool to identify NYU Langone-Brooklyn adult patients that are listed as current smokers in EPIC. If a patient has opted in to being contacted about research studies through MyChart, we will send them a notification (Appendix V) about our study through their MyChart portal. Patients will be able to reach out to our study team directly for screening. Patients who are eligible will be scheduled for consent, and patients who are ineligible will be referred to the NY State Quitline.

Fifth, we will recruit participants in-person by approaching patients in primary care clinic waiting rooms. An RA will identify herself/himself as working on a quit smoking research study, ask if the patient would like to hear more, and then provide the patient with a screening questionnaire to assess eligibility, if interested. If the patient does not fit the eligibility criteria, the RA will thank them and move on to the next person waiting for their clinic appointment. If the person is eligible, the RA will describe the study further and ask if the patient would be interested in enrolling. If the patient is interested in enrolling, the RA will escort the patient to a private room, go through the consent process and baseline survey, and randomize the patient.

Participants will also be recruited through word of mouth referrals. Participants can earn a one-time \$20 referral bonus for an eligible person referred and successfully randomized into this study. This referral process will be detailed in the patient's consent form and explained to participants during their in-person consent appointment.

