4.3 Patient Participant Consent (Process and Documentation)

All participants will sign IRB-approved informed consent forms prior to completing any study procedures. The study coordinator and/or a trained research assistant will review the contents of the consent form and obtain consent from each of the participants, ensuring that each participant is fully informed of the details of the study and minor potential risks. The signed consent forms will be stored in a locked cabinet within a locked office on NYUMC campus. The research records of enrolled participants will be kept for at least six years after the study is over or as long as the sponsor requires them to be kept. All identifiable information from participants who are deemed ineligible or do not want to enroll in the study will be removed from any tracking or RedCap database.

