5.1 Data Analysis

To evaluate the acceptability and feasibility of the integrated intervention, we will calculate the number of counseling sessions completed and satisfaction with treatment, which we will summarize descriptively using count and frequency statistics. We will calculate additional measures of study feasibility and acceptability, including the eligibility rate among people screened, enrollment rate among those eligible, reasons for ineligibility or refusal, and the proportion of participants who would recommend the intervention to other smokers. To estimate the effect of the integrated intervention on outcomes we will use generalized estimating equations (GEE) to model the main effects of time (baseline to 6 and 12 months)

and treatment group, and the interaction of time and treatment, on each outcome. GEE will allow us to determine whether intervention effects are present and whether they change over time.

We will also calculate and sum all time and costs of administering the interventions. Each intervention staff member will record their activity in a web-based intervention tracking system (using REDCap). Staff prospectively input detailed information for a 1-week sample of their activities and associated time required on a monthly basis. Those recording their time and activities have flexibility to add or tailor their entry form to match their exact activities. We will assign a dollar value for each unit of staff time based on the wage and fringe rate of those who perform the activity using regional labor rates from the US Bureau of Labor Statistics. We will also keep track of medications ordered and used by participants, which we will assign a dollar value to using Red Book, a wholesale pharmaceutical pricing index. Once all costs are compiled and summed, they will be adjusted to constant dollars using the medical care component of the Consumer Price Index.

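### The EMR query is repeated over overlapping 12-month windows while identifiers of vetoed, ineligible and declining patients are destroyed, so these patients can be relisted unrecognised

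*Combined protocol and SAP*

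**What the plan says.** The second recruitment method in Section 4.2 uses EMR data to "identify patients who were screened as current tobacco users during a clinical visit in the" "last 12 months". On repetition it says: "We would like this query to be completed 4 times (3 months apart".

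Before any approach, the assigned primary care provider (PCP) is emailed and has 4 business days to object. On an objection: "If a provider tells us not to contact a patient, we will remove the patient from our recruitment list (destroying his/her identifiers". If the provider does not object, a letter and flyer go out and a call follows a week later. Patients with no PCP on record get the mailing at once, without a provider step.

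For people who are screened out or refuse, Section 4.2 says: "All identifiable screener data for patients who are deemed ineligible or who do not wish to participate in the study will be destroyed". What stays is itemized screener data, for which "no PHI will be saved and we will only label participants with a pre-screening number". Section 4.3 extends the deletion: identifiable information on people "deemed ineligible or do not want to enroll in the study will be removed from any tracking or RedCap database".

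Section 5.1 lists feasibility and acceptability measures "including the eligibility rate among people screened, enrollment rate among those eligible", together with reasons for ineligibility or refusal. It gives no rule for a person screened more than once.

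**The concern.** Removing someone from a list protects that person only while the list is not rebuilt, and here it is rebuilt three times. The deletion rule takes away the information needed to honour a veto or a refusal at the next query. The body of the protocol has no suppression key, no de-duplication step and no restriction of later runs to new patients. The date of the smoking screen is among the extracted fields, but no rule uses it to drop repeats. Enrolled patients stay recognisable through the linking file in Section 5.3; the groups whose data are destroyed do not.

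Two things are at stake. The first is respect for opt-outs: a provider who has objected once may reasonably think the matter closed, and a patient who has said no may be written to and called again. The second is the descriptive feasibility results under Aim 1. Someone screened twice would count as two people, and with the link destroyed the duplication could not be found or corrected afterwards.

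**Working it through.** The documents give no overlap or duplicate figure, so there is nothing to reproduce. The steps below show what the stated intervals imply.

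**Inputs from Section 4.2:** look-back 12 months; four queries, taken at months 0, 3, 6 and 9.

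**Assumptions:** each run covers the 12 months before its own date; each patient has one qualifying screening date; dates are evenly spread. Further visits would raise the overlap.

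**1. Relisting.** The share of list 1 still inside the window is (12 − 3)/12 = 75% at query 2, (12 − 6)/12 = 50% at query 3 and (12 − 9)/12 = 25% at query 4. The four windows total 4 × 12 = 48 window-months over 12 + 9 = 21 distinct months. That is 48/21 = 2.29 listings per person, and 1 − 21/48 = 56% of listed rows are repeats. These figures count listings before any veto, refusal or enrollment is acted on.

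**2. Contact after a veto.** A quarter each of list-1 patients are relisted 0, 1, 2 or 3 times. Let p be the chance that a provider who objected before fails to do so again in time, independently at each query. The documents give no p. The chance of later contact is 0.25 × Σ[1 − (1 − p)^k] over k = 0 to 3:

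- p = 0.10: 0.25 × (0 + 0.10 + 0.19 + 0.271) = 14%
- p = 0.20: 0.25 × (0 + 0.20 + 0.36 + 0.488) = 26%
- p = 0.40: 0.25 × (0 + 0.40 + 0.64 + 0.784) = 46%

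This covers list-1 patients with a PCP. Patients first listed later have fewer relistings, and those first listed at query 4 have none.

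**3. Feasibility rates.** With lists of size N, there are N + 3 × 0.25N = 1.75N people and 4N − 1.75N = 2.25N repeat listings, or 2.25/1.75 = 1.286 repeats per person. Let r be the share of repeat listings of already screened people that end in another screen. The documents give no r.

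- Eligibility rate, true value E, only ineligible people re-screened: E / [E + (1 − E)(1 + 1.286r)].
- Enrollment rate, true value e, eligible decliners re-screened and declining again: e / [e + (1 − e)(1 + 1.286r)].

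| r | True 50% is reported as (either formula) |
|---|---|
| 0 | 50.0% |
| 0.10 | 47.0% |
| 0.25 | 43.1% |
| 0.50 | 37.8% |

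The two effects partly offset in the eligibility rate, because a re-screened decliner counts again as eligible. With E = e = 0.5 and the same r in both groups, the eligible count is 0.5(1 + 0.5 × 1.286r) and the ineligible count is 0.5(1 + 1.286r). The reported eligibility rate is then 48.5%, 46.8% or 44.6% at r = 0.10, 0.25 or 0.50. All of these are illustrations for the EMR route alone.

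**The case against.** The strongest reply is that Section 4.2 never says each run returns the full rolling 12 months without removing earlier names. The extracted screening date would allow later runs to be limited to new dates. This stands to the extent that reappearance is possible rather than certain. It does not close the gap, because repeating the same query most naturally means the same look-back, and no limiting rule is written.

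Several stronger readings are tempting but not supported:

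- *That the veto is cancelled.* As written, a relisted patient with a PCP goes through the provider email and the 4-business-day wait again. The veto has to be repeated; it is not overridden. The weaker position is that of decliners, whose own refusal triggers nothing, and above all of decliners without a PCP, for whom there is no check at all.
- *That everyone relisted distorts the rates.* Listing is not screening. Vetoed patients, and those who decline before screening, enter neither the eligibility nor the enrollment rate. The 2.29 listings per person therefore say nothing direct about those rates.
- *That repeat contact is a study-related adverse event.* Sections 5.2 and 6.2 treat violations of privacy or confidentiality that way, but nothing there says a second recruitment letter or call is such a violation.

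Two limits also stand. EMR outreach is one of five recruitment methods. And the recruitment letter, phone screener and provider email are appendices not included in the document reviewed, so opt-out wording in them can be neither confirmed nor excluded.

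**Conclusion.** The gap is real and should be closed. On the natural reading of Section 4.2, vetoed, ineligible and declining patients can return on later lists, and the deletion rules in 4.2 and 4.3 leave the study team no stated means of recognising them. This is more than missing detail, because the deletion rule itself removes what would be needed to honour the opt-out.

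The 75%, 50% and 25% relisting figures rest on the full look-back and on evenly spread single screening dates. The 14% to 46% range for contact after a veto also rests on assumed, independent provider non-response and is not an estimate. The 5.1 rates can be biased downward, and the bias would be undetectable. It is zero if nobody is re-screened, and its size cannot be fixed from the documents. Randomization and the GEE comparison of the arms are not touched.

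**What to change.** In Section 4.2, adopt one of two rules:

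- State that queries 2 to 4 return only patients not returned by an earlier query, and that DataCore keeps the list of earlier returns for this purpose. The protocol says only that DataCore will request the report, so retention has to be written in.
- Keep a restricted, coded do-not-contact key with no clinical data, match each new list to it before any email or letter, and destroy it after the fourth query. A record number is not among the fields listed for extraction, so the protocol must say what the key is built from.

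In Section 5.1, count screened and eligible people once per unique person on the EMR route.

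The cost is an added line in the data request and a short amendment. Under the first rule, people ineligible earlier are not re-approached by this route, though flyers and referrals stay open to them. Under the second, a coded key is held for about 9 months (three intervals of 3 months), and the destruction wording in 4.2 and 4.3 must be changed to match. Either rule should be in place before identifiers from the first list are destroyed, since links lost then cannot be rebuilt by the study team.

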4.3 Patient Participant Consent (Process and Documentation)

All participants will sign IRB-approved informed consent forms prior to completing any study procedures. The study coordinator and/or a trained research assistant will review the contents of the consent form and obtain consent from each of the participants, ensuring that each participant is fully informed of the details of the study and minor potential risks. The signed consent forms will be stored in a locked cabinet within a locked office on NYUMC campus. The research records of enrolled participants will be kept for at least six years after the study is over or as long as the sponsor requires them to be kept. All identifiable information from participants who are deemed ineligible or do not want to enroll in the study will be removed from any tracking or RedCap database.

4.4 Patient Participant Baseline Interview

After obtaining informed consent, a RA will administer a baseline survey (Appendix D) assessing sociodemographics, tobacco use, motivations and readiness to quit, income, financial stress, mood, household spending patterns and other intervention covariates or mechanisms.

4.5 Patient Participant Randomization

At the conclusion of the baseline survey, the RA will open a study database on a computer that he/she will have at the time of informed consent and enter a randomly assigned study ID number. The database will then use a random-number generator (developed under the supervision of the statistician) to assign the patient participant to one of the study arms. The database will store the randomization results and display the results on the screen for the RA, who will inform the participant of his/her group assignment, discuss the details of the assigned intervention, and schedule the patient participant for his/her intervention's first session and follow-up assessments.

4.6 Patient Participant Intervention Delivery

4.6.1 Intervention Arm: Integrated Smoking Cessation and Financial Counseling

Participants randomized to the Intervention Arm will receive counseling that integrates financial counseling and smoking cessation counseling immediately after enrolling in the study. The goal of the financial counseling will be presented to participants as helping them enroll in government assistance programs when needed and helping them manage their funds better to have more for things that make them happy and to improve their quality of life and well-being. The counseling content will be as follows:

Session 1: Session 1 will be in-person and will focus on a tobacco use intake and financial planning and will be comprised of three main components: (1) screening and referral for financial assistance programs, (2) money management counseling and (3) tobacco use and cessation overview. The designated study site-counselor will help the patient participant complete two online surveys assessing their eligibility for New York State and federal benefits. These assessments are provided free to the public through the www.mybenefits.ny.gov (state) and www.benefits.gov (federal) websites and take approximately 10 minutes each to complete. The websites will provide patients with a list of benefits to which they may be eligible with instructions on how to enroll. The counselor will also provide patients with an overview of programs available in New York City (e.g., financial empowerment counseling, housing assistance) and refer the patient to the program when appropriate. Patient participants will have the option to call the counselor in between sessions with follow-up questions or to request assistance in completing online applications for benefits.

Second, the counselor will initiate money management counseling. [name], a collaborator on the project, will train all study counselors in financial counseling prior to the first counseling sessions. [name] will not have access to PHI, but will act as a consultant to the study team regarding any issues that pertain to the financial counseling aspect of the study. Participants will first describe their longer-term goals, and based on these longer-term goals, will be encouraged to set shorter-term financial goals for their money management. Next, participants will, assisted by a timeline follow-back calendar, complete an inventory describing their sources of income, expenditures (both monetary and in-kind), debts and asset balances. Based on this inventory, participants will be asked to make a budget based on smoking cessation at the time of their future quit date. This budget will list planned expenditures, with those made possible by smoking cessation highlighted and listed separately to increase their saliency and reward value.

Lastly, the counselor will complete a tobacco use intake and brief counseling (Appendix H) with the participant. Topics covered will include: 1) Assessment of smoking and quitting history, 2) Assessment of current readiness to quit through ratings of “importance” and “confidence”, 3) Strategies to raise importance and confidence ratings, 4) Preparations for quitting, 5) Identification of top barriers toward quitting and smoking triggers, as well as coping strategies to address each trigger, 6) NRT use and barriers to use, and 7) Setting a quit date in the next 30 days. Participants will receive a flyer (Appendix Q) on how to use NRT and its possible risks and side effects.

Session 2 (See Appendix H, p. 17): Session 2 will be completed in-person and will begin with follow-up on the prior session’s financial counseling to assess short-term goals (e.g., enroll in benefits) and challenges, and then will transition to focus on smoking cessation. Topics covered will again include: 1) Assessment of smoking and quitting history, 2) Assessment of current readiness to quit through ratings of “importance” and “confidence”, 3) Strategies to raise importance and confidence ratings, 4) Preparations for quitting, 5) Identification of top barriers toward quitting and smoking triggers, as well as coping

strategies to address each trigger, 6) NRT use and barriers to use, and 7) Setting a quit date in the next 30 days.

Sessions 3 – 9 (See Appendix H, p. 23): Sessions 3-9 can be either in-person or over the phone (depending on patient preference). The counselor will deliver financial counseling prior to the smoking cessation counseling in order to motivate participants to attend to the quitting. Participants will track their progress towards adhering to the budget by reviewing financial transactions during the preceding week, and adjusting their budgets if the original budgets proved to be unrealistic. Tobacco expenditures and savings will be highlighted and tracked separately to increase their saliency and reward or cost value.⁶⁴ The composition of the tobacco cessation counseling during these later sessions will depend on each patient's individual quit progress.

